7.6. Handling of Dropouts or Missing Data

Where individual data points are missing because of insufficient samples, dropouts, or other reasons, the data will be analyzed based on reduced denominators (e.g., using the response evaluable population). For survival analysis, dropouts without confirming events will be treated as censored.

All missing and partial start dates will be queried for a value. If a complete start date cannot be obtained, the following imputation rules apply in order to calculate duration of adverse event, concomitant medication use, or prior cancer history endpoints:

- Missing month and day
 - If the year of the incomplete start date is the same as the year of the date of study drug administration, then the missing month and day of the start date will be imputed to be the month and day of the start of study drug administration.
 - If the year of the incomplete start date is before the year of the date of study drug administration, December 31 will be assigned to the missing fields.
 - If the year of the incomplete start date is after the year of the date of study drug administration, January 1 will be assigned to the missing fields.

- Missing month only
 - If only the month is missing, the day will also be treated as missing, and both month and day will be replaced according to the above procedure.
- Missing day only
 - If the month and year of the incomplete start date are the same as the month and year of the date of study drug administration, the start date of study drug will be assigned to the missing field (i.e., AEs will be assumed treatment-emergent, and medications will be assumed concomitant).
 - If the month and year of the incomplete start date are before the month and year of the date of study drug administration, the last day of the month will be assigned to the missing field.
 - If the month and year of the incomplete start date are after the month and year of the date of study drug administration, the first day of the month will be assigned to the missing field.

If the stop date is complete and the imputed start date, when imputed as instructed above, is after the stop date, the start date will be imputed to equal the stop date.

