8.3. Demographics and Baseline Characteristics

Descriptive statistics will be used to summarize demographics and baseline characteristics for the Safety Population.

Subject demographics and baseline characteristics including age, sex, race, ethnicity, height, weight, and Eastern Cooperative Oncology Group (ECOG) performance status will be summarized by study part.

Medical and surgical history/physical findings will be coded using MedDRA Version 25.1 and summarized by system organ class (SOC)/ preferred term (PT) and study part. Cancer history at screening will be summarized by diagnosis and stage for each study part. Previous anti-cancer therapy, prior cancer surgery, and prior radiation therapy will be summarized by study part and tumor type. Previous anti-cancer therapy will be further categorized as the number and percentage of subjects having any platinum-based antineoplastics, vinca alkaloid therapies, anti-PD-1 agents, or other prior anti-cancer therapies. These summaries will include summary statistics of prior regimens per subject, best overall response, number experiencing peripheral neuropathy (platinum-based antineoplastics only), and number resistant to the therapy (platinum-based antineoplastics and vinca alkaloids only).

Duration on last prior therapy will be calculated as the earliest of Progression Date on prior therapy, Last Date on prior Treatment, or Date of IT-01 Screening less the earliest Treatment Initiation Date of Most Recent Prior Cancer Therapy, converted to months by dividing by 30.4375. A separate tornado plot will present duration on last prior therapy vs. duration on INT230-6 for Cohorts A/B1/EA/EC, EC2/EC3, DEC/DEC2 and FEC.

Listings will be provided for individual subject demographics and baseline medical and surgical history/physical findings, as well as cancer history at screening, previous anti-cancer therapy, prior cancer surgery and prior radiation.

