6. IMPUTATION OF END DATE OF LAST PRIOR ANTI-CANCER THERAPY

- If end date is completely missing, use IT-01 screening date
- If year is present and end month is missing, use the min of (IT-01 screening date, last date of year)
- If month is present and day is missing, use the min of (IT-01 screening date, last date of month)

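### A partial start date for the last prior therapy is set to its latest day, which cuts that subject's prior-therapy duration by up to about 12 months, or to zero

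*SAP*

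**What the plan says.** SAP 8.3 defines the variable: "Duration on last prior therapy will be calculated as the earliest of Progression Date on prior therapy, Last Date on prior Treatment", or the IT-01 screening date, "less the earliest Treatment Initiation Date of Most Recent Prior Cancer Therapy, converted to months by dividing by 30.4375". It then says: "A separate tornado plot will present duration on last prior therapy vs. duration on INT230-6", for each of the four treatment groups.

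SAP 7.6 has partial start dates queried first. Where the query fails, "the following imputation rules apply in order to calculate duration of adverse event, concomitant medication use, or prior cancer history endpoints". The rules are:

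- Year-only start in an earlier year: when the year is "before the year of the date of study drug administration, December 31 will be assigned to the missing fields".
- Year-only start in the first-dose year: "the missing month and day of the start date will be imputed to be the month and day of the start of study drug" administration.
- Day missing, month earlier than the first-dose month: last day of that month.
- Where the stop date is complete and the imputed start "is after the stop date, the start date will be imputed to equal the stop date".

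SAP Appendix 1 item 6 covers the end date of the last prior therapy: "If year is present and end month is missing, use the min of (IT-01 screening date, last date of year"). A month-only end gets the last day of the month under the same screening cap. A wholly missing end becomes the screening date. Item 6 gives no start-date rule.

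**The concern.** The 7.6 rules are built to classify events. Placing a doubtful start late, or on the first-dose date, settles whether an adverse event counts as treatment-emergent or a drug as concomitant. For a duration the same choice gives the shortest prior therapy that the partial start allows, and can give zero. The INT230-6 bar comes from study dosing records and is unaffected, so it looks longer beside a shortened prior-therapy bar.

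The study is open-label and non-randomised. This plot is the SAP's planned display of time on INT230-6 against the same subject's previous treatment, so a reader may give it weight that a demographic table would not get. A bar set to zero by rule makes any time on INT230-6 look like a gain.

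**Working it through.** The SAP gives no figure for this point, so there is none to reproduce. The check is date arithmetic with the 8.3 formula: (end date − start date) / 30.4375 months.

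**Largest shift.** 1 January moved to 31 December is 364 days (365 in a leap year): 364 / 30.4375 = 11.96 months. For a missing day the most is 30 days: 30 / 30.4375 = 0.99 months.

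**Single cases, start known only by year, stop complete**

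- Start 2018, stop 15 June 2019. Imputed: 31 December 2018 to 15 June 2019 = 166 days = 5.45 months. Earliest possible start: 1 January 2018, 530 days = 17.41 months. The centre of that range is (5.45 + 17.41) / 2 = 11.43.
- Start 2018, stop 15 November 2018. The imputed start passes the stop, so the duration is 0. The possible range is 0 to 318 days = 10.45 months.
- True dates 10 January to 10 April 2019 (2.96 months), first dose 15 June 2019. The year-only start becomes 15 June, after the stop, so the duration is 0. Protocol 6.1 item 9 requires prior chemotherapy or immunotherapy to end at least 4 weeks before dosing (2 weeks for short half-life drugs). For such therapy, a year-only start in the first-dose year with a complete stop therefore always gives 0.

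**When the end date is partial too.** The correction setting start equal to stop needs a complete stop date, so it does not apply.

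- Both dates known only as the same earlier year: both become 31 December, duration 0. If the two dates were uniform in the year (an assumption), the expected gap would be 12 / 3 = 4 months.
- The 2019 case above with a year-only end and screening on 25 May 2019 (assumed 21 days before dosing): start 15 June, end 25 May, so −21 / 30.4375 = −0.69 months. No rule handles this.

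**Average effect by pattern.** This is a simulation with 40,000 subjects per scenario. Assumptions, none of them from the documents: first dose uniform over 2018–2021, screening 1–28 days before it, prior therapy ended 28–180 days before first dose, no earlier progression date. Entries are mean imputed months.

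| Partial dates | True 3 | True 6 | True 12 |
|---|---|---|---|
| Start year-only, end complete | 0.37 | 1.49 | 6.02 |
| Start day missing, end complete | 2.50 | 5.49 | 11.51 |
| Both year-only | 0.88 | 2.83 | 8.49 |
| Both day missing | 2.98 | 5.97 | 11.98 |
| Start complete, end year-only | 5.47 | 8.46 | 14.48 |

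In the first row, 76%, 50% and 0.1% of subjects get exactly zero. In the third row, 51%, 25% and 0% get a negative duration.

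**The case against.** **The end-date rule works the other way.** Appendix 1 item 6 takes the latest day, which lengthens prior therapy. A complete 6-month course with a year-only end becomes 8.46 months on average, and with the day missing on both dates the two rules roughly cancel. This stands. A reader might infer that the plot as a whole is biased toward INT230-6. The documents do not support that, because the net direction depends on the mix of missing starts and ends, which they do not give. The offset is partial where both dates are year-only, and 8.3's choice of the earliest of three end dates limits it further.

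**Scope.** SAP 8.3 treats cancer history (diagnosis and stage) separately from previous anti-cancer therapy, so 7.6 might mean only the former. That is possible. But duration on last prior therapy is the only prior-cancer duration the SAP defines, and no other start-date rule for it is visible; item 8 in the contents list repeats item 6's end-date title. If the narrow reading is right, the start date has no rule at all, and one still has to be written.

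**Weight.** A reader might also treat the plot as the trial's efficacy comparator. It is not presented as one. It sits under demographics and baseline characteristics, outside the Table 2 endpoints and Section 9, with no test or decision attached. Time on INT230-6 is itself limited by schedule (Days 0 to 56 in the E cohorts and 0 to 112 in A1/B1, Protocol 12.1.3.1, with maintenance only in the 175 mL cohorts), which can make INT230-6 look shorter.

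**Frequency.** Dates are queried first, only the most recent therapy matters, and nothing in the documents says partial dates are common. With only the day missing, the loss is about half a month on average.

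**Conclusion.** The point holds for subjects with a partial prior-therapy start and a complete stop. Their prior-therapy duration is shortened by up to about 12 months (year-only) or 30 days (day only), and is zero whenever the imputed start passes the stop. For these subjects the plot is tilted toward INT230-6. This rests on reading 7.6's prior cancer history wording to include the 8.3 duration.

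Across all subjects the bias has no established direction or size. Two rules pull one variable in opposite directions. With day-only gaps on both dates they roughly cancel. With year-only gaps on both, the duration is still shortened on average under the stated simulation assumptions, and negative values can arise. The issue is worth correcting in a descriptive figure; it does not affect the trial's endpoints.

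**What to change.** State in SAP 7.6 that its rules do not apply to prior-therapy start dates, and extend Appendix 1 item 6 to cover both dates:

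- **End date.** Year-only: July 1. Month-only: the 15th. If later, use the midpoint between the earliest possible start and the latest possible end. Cap at the screening date. The midpoint clause is needed because a known October start with a year-only end would otherwise come out negative. A wholly missing end stays at screening, as now.
- **Start date.** Year-only: July 1. Month-only: the 15th. If earlier, use the midpoint between the earliest possible start and the end date used in 8.3. This covers every case where the default start would fall on or after the end, so no duration is negative or forced to zero.
- **Display.** Mark imputed bars, report how many there are, and repeat the plot with complete dates only.

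For the first case in the working (start 2018, stop 15 June 2019), the start becomes July 1 2018: 349 / 30.4375 = 11.47 months, against 5.45 now. A simpler version (July 1 or the 15th for the start, capped at a complete end date) gave simulated means of 3.38, 6.00 and 12.03 months for true durations of 3, 6 and 12 with year-only starts, and 3.01, 6.00 and 12.02 with the day missing.

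The cost is a few appendix lines and a little programming, with no new data. Bars with partial starts get longer. Bars with partial ends get shorter, which moves those subjects toward INT230-6. SAP Section 2 requires the plan to be final before database lock, so the rule should be settled by then.

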7.7. Outlier Handling

Potential data entry errors manifested as outliers will be handled in the data management process through edit checks.

7.8. Adjustments for Covariates

There is no plan to adjust for any covariates.

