3. STUDY OBJECTIVES AND ENDPOINTS

3.1. Research Hypothesis

INT230-6 when administered intratumorally (IT) to one or more tumors at an optimal dose to tumor volume ratio (i.e., greater than 1 mL per 4 cc of tumor) while treating a sufficient amount of the visible disease will safely reduce tumor burden, stabilize disease, promote an immune response against the cancer, and extend overall survival.

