7.5. Examination of Subgroups

Analysis endpoints of safety and efficacy variables may be further explored with the following subgroups:

- Tumor ratio (1:4, 1:3, 1:2 or dose set by longest diameter formulas)
- Dose schedule (every 2 weeks versus every 4 weeks)
- Superficial tumor injection subjects versus deep tumor injection subjects
- Tumor type (Sarcoma)
- Status of prior treatment with platinum-based antineoplastics or vinca alkaloid therapies
- Subjects with less than 2 tumors injected compared to those with ≥ 2 tumors
- Tumor burden: subjects receiving $\geq 40\%$ of tumor burden injected versus those receiving $< 40\%$; tumor burden is calculated based on EDC documentation of target, bystander, non-target, and new tumors. Subjects receiving $\geq 40\%$ of baseline total tumor burden injected overall (during the course of therapy) and at first dose will be explored. For overall, the sum of all injection volumes will be used in the calculation.

The subgroups to be analyzed for each endpoint are described in Section 8, Section 9, and Section 10.

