9.2. Progression-Free Survival and Overall Survival

Progression free survival (PFS) and Overall Survival (OS) will be evaluated for the All Treated Population, the REP, and the SEP. PFS will be defined as the time (in months) from first dose of INT230-6 to either observation of clinical deterioration, removal from study, or occurrence of death due to any cause within 126 days (approximately 2 time intervals for tumor assessments) of the last tumor assessment. Progression date will be defined as the end of treatment date as captured per eCRF guidelines when the reason for end of treatment is either 'Radiographic

deterioration' or 'Clinical deterioration.' In subjects without a progression date or with a death date more than 126 days after the last tumor assessment, the PFS time will be censored on the date of last tumor assessment or last treatment date if the subject has no post-baseline tumor assessments. PFS analyses will consider tumor assessments after treatment discontinuation.

OS will be defined as the time (in months) from first dose of INT230-6 to death. Subjects for whom death is not reported will be censored at the date of end of study.

PFS and OS will be summarized in a listing. The median time to OS as obtained from Kaplan-Meier methods will be tabulated by subgroup and will include the median, 25th percentile, 75th percentile, and a 2-sided point-wise 95% confidence interval. Hazard ratios may be determined between certain curves for the Kaplan Meier figures noted below.

A Kaplan Meier figure of OS for the All Treated, REP, and SEP populations will be presented for each of the following:

- a curve all treated monotherapy patients, a curve for subjects that received a dose to total tumor burden < 40% of tumor burden, a curve for those subjects that had a dose to total tumor burden \geq 40%,
- a curve for escalation cohort combining A1, B1, EA, EC, and a curve for escalation cohort combining EC2 and EC3,
- a curve for sarcoma patients in the monotherapy cohort and a curve for monotherapy sarcoma patients having \geq 40% of their total tumor burden treated,
- a curve for the pembrolizumab DEC/DEC2 combined cohort for subjects,
- a curve for all ipilimumab FEC cohort subjects,
- a curve for the ipilimumab FEC sarcoma subjects, a curve for all monotherapy sarcoma patients and a curve for monotherapy sarcoma subjects having \geq 40% of their total tumor burden treated will be included.

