1. TOTAL TUMOR BURDEN (TTB)

Step 1: If all 3 dimensions are reported, volume = (longest*shortest*depth*0.63)

Step 2: If not all 3 dimensions are reported and longest diameter is reported, volume calculation is based on the longest diameter measurement.

1. If $. < \text{longest} < 1.5 \text{ cm}$, volume = 1 cm^3
2. If $1.5 \leq \text{longest} \leq 4 \text{ cm}$, volume = $\text{longest}^3/2$
3. If $4 < \text{longest} < 9 \text{ cm}$, volume = $\text{longest}^3/3$
4. If $\text{longest} \geq 9 \text{ cm}$, volume = $\text{longest}^3/4$
5. If shortest is only measurement reported, Diameter = shortest and follow step 2 tasks 1 to 4 for volume calculations

Step 3: Sum all calculated volume values across target and bystander tumors.

2. % DOSED TTB

Step 1. Calculate TTB of all of a patient's bystander and target tumors reported in the database using the TTB formulas above.

Step 2. Calculate patient's cumulative dose of INT230-6

Step 3. Calculate % Dosed TTB as (cumulative dose / Patient TTB) * 100.

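### The below-40% dosed-TTB group is enriched for large baseline burdens and early stoppers, so the unadjusted <40% versus ≥40% survival comparison can favor ≥40% even if the drug is inert

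*SAP*

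**What the plan says.** SAP 3.1 hypothesizes that intratumoral dosing at an adequate ratio, "while treating a sufficient amount of the visible disease will safely reduce tumor burden", and will also extend overall survival (OS).

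SAP 9.2 takes this up with Kaplan-Meier OS curves for monotherapy subjects: all of them, those below 40%, and "a curve for those subjects that had a dose to total tumor burden" of at least 40%. It adds: "Hazard ratios may be determined between certain curves for the Kaplan Meier figures noted below". For monotherapy sarcoma it plots all subjects and the ≥40% subset, with no below-40% curve. OS runs from first dose.

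The grouping variable is in SAP Appendix 1, item 2: "Calculate % Dosed TTB as (cumulative dose / Patient TTB) * 100". SAP 7.5 says of the dose: "For overall, the sum of all injection volumes will be used in the calculation". It also mentions a version based on the first dose only.

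TTB is described in two ways. Appendix 1, item 1 says: "Sum all calculated volume values across target and bystander tumors". SAP 7.5 says: "tumor burden is calculated based on EDC documentation of target, bystander, non-target, and new tumors".

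SAP 7.8 says: "There is no plan to adjust for any covariates". Neither 7.5 nor 9.2 describes a burden-stratified, landmark or time-varying version of the 40% comparison.

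**The concern.** A subject reaches 40% by having little tumor to divide by, by receiving many injections, or both. Neither is an effect of the drug.

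- **Burden path.** Session volumes are capped by cohort, so a large enough baseline TTB puts 40% out of reach. If burden predicts death, the below-40% curve falls faster whatever the drug does.
- **Time path.** Dose accumulates after the OS clock starts, so a subject must usually survive and stay on treatment for several sessions to enter the ≥40% group.

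Because the comparison bears directly on the SAP's dose-sufficiency hypothesis, a gap between the curves would be easy to read as evidence that treating enough of the tumor prolongs life.

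**Working it through.** **The plan's own figure.** The only worked value is the example at the end of SAP Appendix 1. TTB = 22.68 + 1.89 + 1.26 + 1.134 = 26.964 cc, and (20 + 2)/26.964 = 81.6%, printed as about 81.5%. The doses in the example's prose (20 and 1 mL) give 21/26.964 = 77.9%. The example is therefore inconsistent, but the formula is clear. No group size, event count or target hazard ratio is stated for the 40% comparison.

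**Step 1: largest TTB that can reach 40% in five doses.** Caps are from Protocol Tables 4, 5, 6, 7a and 7b and section 5.2. Ceiling = sum of caps / 0.40.

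| Cohort | Ratio | Session caps (mL) | Sum (mL) | Ceiling (cc) |
|---|---|---|---|---|
| A1 | 1:4 | 5, 10, 15, 15, 15 | 60 | 150 |
| B1 | 1:4 | 5, 15, 30, 30, 30 | 110 | 275 |
| EA | 1:4 | 20, 20, 30, 30, 30 | 130 | 325 |
| EC | 1:2 | 30, 60, 120, 120, 120 | 450 | 1,125 |
| EC2 | 1:3 | 100, 130, 160, 190, 220 | 800 | 2,000 |
| EC3 | 1:3 | 175 × 5 (induction) | 875 | 2,187.5 |

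At each ceiling the cap is the limit, not the ratio (A1: 150 × 0.25 = 37.5 mL against a cap of at most 15 mL). Per-tumor limits lower the ceiling for a single tumor. In B1, (5 + 10 + 3 × 15)/0.40 = 150 cc; in EA, (10 + 10 + 3 × 20)/0.40 = 200 cc. By Appendix 1's longest-diameter rule an 8 cm tumor is 8³/3 = 171 cc, which is out of reach in A1 and B1 if it is the only tumor.

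**Step 2: where the caps matter.** In EC3 the session cap binds only above 175 × 3 = 525 cc. Below that, the percentage depends on the number of sessions and the fraction injected.

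**Step 3: sessions needed.** One full dose at 1:4 or 1:3 gives at most 25% or 33.3%, so 40% takes at least two sessions. The exception is EC, where dose 1 suffices only if TTB ≤ 30/0.40 = 75 cc. For the same reason the first-dose version in SAP 7.5 cannot replace the overall one.

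**Step 4: simulation with an inert drug.** Assumptions, none from the documents except the caps, the ratios and the 8-week life-expectancy criterion: lognormal TTB; one eighth of subjects in each of A1, B1, EA and EC and one quarter in each of EC2 and EC3; exponential OS with median 9 months; every tumor injected at ratio; per-tumor limits and retreatment ignored.

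With median TTB 100 cc, log-SD 1.2 and five doses for all, ≥40% holds 81% of low-loading and 99% of EC2/EC3 subjects. Median TTB is 84–87 cc in the ≥40% group and 416–467 cc below 40%, but only 55% of the ≥40% group lies below the overall median.

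Hazard ratio, ≥40% versus <40%:

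| Dosing | Hazard per TTB doubling | Unadjusted | With log(TTB) |
|---|---|---|---|
| All five doses | 1.0 | about 1 | – |
| All five doses | 1.15 | 0.64–0.74 | about 0.9–1.06 |
| All five doses | 1.3 | 0.42–0.65 | about 0.9–1.06 |
| Stops at half of survival time | 1.0 | 0.65 | 0.60 |
| Stops at half of survival time | 1.15–1.3 | 0.41–0.48 | 0.60–0.66 |

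The unadjusted five-dose ranges span assumed median TTB of 50–250 cc. The early-stopping rows use a 56-day survival floor.

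Share of 60-subject data sets showing benefit at two-sided p < 0.05 (nominal 2.5% in that direction), unadjusted then TTB-adjusted:

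- five doses: 18% then 4% (1.15-fold); 31% then 1.5% (1.3-fold)
- early stopping: 20% then 22% (1.0); 46% then 23% (1.15); 67% then 21% (1.3)

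Monte Carlo noise is roughly ±0.15 on the hazard ratios. The 60-subject rates use 204–279 usable replicates of 300, because runs with fewer than five subjects in a group were dropped.

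**The case against.** - **The comparison is exploratory.** OS is an exploratory objective, the hazard ratios are optional, and no test or alpha is stated. This stands. The simulated rejection rates show how easily chance and bias could mislead; they are not error rates of a planned test.
- **The caps do not bite everywhere.** This stands. A reader might infer that ≥40% is simply the small-burden group by construction. The caps do not support that for the pooled comparison: the EC2 and EC3 ceilings are 2,000 cc or more, and the ≥40% group is close to evenly split around the overall median TTB.
- **The ceilings are idealized.** Under Protocol 5.2 and 5.5 investigators choose the tumors and need not inject each one every session. Volumes fall as tumors shrink (8.10), while maintenance and retreatment add dose. This stands: the ceilings are not hard limits. It does not take TTB out of the denominator. In the early-stopping setting with 20–100% of tumor injected, the unadjusted hazard ratio was 0.49–0.68 and the adjusted 0.64–0.65.
- **Adjusting for TTB does not cure the comparison.** This stands and shapes the fix. The early-stopping rows show a TTB-adjusted hazard ratio that is still clearly below 1.
- **Overlap may be thin.** Within a capped cohort the two groups may share little TTB range, and few EC2/EC3 subjects fall below 40%. This stands as a limit on any adjusted estimate.

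**Conclusion.** The concern holds in this form. Baseline TTB is the denominator of the grouping variable, session caps push large burdens below 40% in A1, B1 and EA (less in EC, rarely in EC2/EC3), and early stoppers also collect there. With no adjustment planned, the curves and any hazard ratio can favor ≥40% for an inert drug. With the burden path alone, the null hazard ratio is about 0.64–0.74 or 0.42–0.65 under the two assumed prognostic strengths.

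These sizes rest on assumed values for the prognostic effect of TTB, its distribution and the cohort mix. If burden is not prognostic, the burden path vanishes and only the time path remains.

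Two further readings are tempting but unsupported. A reader might infer that SAP 7.8 forbids adjustment; it only states that none is planned. A reader might also infer that adding log(TTB) makes the comparison valid; it removes the burden path but not the bias from defining groups by dose given after first dose. The risk is misreading of an exploratory result, and the remedy is inexpensive.

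**What to change.** 1. **Settle the TTB definition first.** Reconcile SAP 7.5 (non-target and new tumors included) with Appendix 1 (target and bystander only), and use baseline measurements only. Counting new tumors would enlarge the denominator in progressing subjects.
2. **SAP 7.8 and 9.2.** Report any <40% versus ≥40% monotherapy hazard ratio from a Cox model with log(baseline TTB) as a covariate, stratified by low/high loading group where both dose groups are represented. Show the TTB distribution and overlap by group.
3. **Handle dose given after time zero.** Combine the model with a landmark, counting dose only up to it, or with time-varying cumulative dose. A landmark can leave residual bias if stopping is itself prognostic. Do not present the TTB-adjusted hazard ratio alone as corrected.
4. **Sarcoma.** If a hazard ratio is reported, compare ≥40% with <40%, not with the overlapping all-sarcoma group.
5. **Labeling.** Mark the unadjusted curves as confounded by baseline burden and treatment duration.

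The cost is SAP wording and a small amount of modeling. Baseline TTB, cumulative dose and dose category are already listed per subject under SAP 9.1. The price is a wider interval, and reliance on the log-linear form where TTB overlap is thin.
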